3.2 Exclusion Criteria

3.2.1 No evidence of CRAB criteria* or new criteria of active MM which including the following:

- Increased calcium levels (corrected serum calcium >0.25 mmol/dL $\{>1\text{mg/dL}\}$ above the upper limit of normal or >2.75 mmol/dL $\{11\text{mg/dL}\}$) related to MM
- Renal insufficiency (attributable to MM)
- Anemia (Hb 2g/dL below the lower limit of normal or $<10\text{g/dL}$) related to MM
- Bone lesions (lytic lesions or generalized osteoporosis with compression fractures)
- Bone marrow plasma cells $>60\%$
- Serum involved/uninvolved FLC ratio ≥ 100 , provided the absolute level of the involved free light chain is at least 100 mg/L and repeated twice (light chain smoldering myeloma as described in section 2.4 is not an exclusion criteria).
- MRI with two or more focal lesions that are at least 5 mm or greater in size

**Participants with CRAB criteria that are attributable to conditions other than the disease under study may be eligible*

3.2.2 Other concurrent chemotherapy, immunotherapy, radiotherapy, or any ancillary therapy considered investigational. Prior therapy with bisphosphonate is allowed. Prior therapy for smoldering myeloma MM may not be an exclusion criterion, discussion with Principal Investigator must occur before enrolling patients with prior treatments. Prior radiation therapy to a solitary plasmacytoma is allowed. Patients who received prior therapy due to being incorrectly diagnosed as having overt multiple myeloma may not be excluded after discussion with the overall PI.

3.2.3 Serious medical or psychiatric illness likely to interfere with participation in this clinical study.

3.2.4 Diagnosed or treated for another malignancy within 2 years of enrollment, with the exception of complete resection of basal cell carcinoma or squamous cell carcinoma of the skin, an in situ malignancy, or low-risk prostate cancer after curative therapy.

3.2.5 Uncontrolled intercurrent illness including, but not limited to, ongoing or active infection, symptomatic congestive heart failure, unstable angina pectoris, cardiac arrhythmia, or psychiatric illness/social situations that would limit compliance with study requirements.

CONFIDENTIAL

This document is confidential. Do not disclose or use except as authorized.

- 3.2.6 Autoimmune disease: Patients with a history of inflammatory bowel disease, including ulcerative colitis and Crohn's Disease, are excluded from this study, as are patients with a history of symptomatic disease (eg, rheumatoid arthritis, systemic progressive sclerosis [scleroderma], systemic lupus erythematosus, autoimmune pneumonitis, autoimmune vasculitis [eg, Wegener's Granulomatosis]) and motor neuropathy considered of autoimmune origin (e.g. Guillain-Barre Syndrome and Myasthenia, Gravis). Patients with Hashimoto's thyroiditis are eligible to go on study.
- 3.2.7 Pregnant or nursing women will be excluded from the study because lenalidomide is an agent with the potential for teratogenic or abortifacient effects.
- 3.2.8 History of severe allergic reactions attributed to compounds of similar chemical or biologic composition to Nivolumab or lenalidomide.
- 3.2.9 Known seropositive for or active viral infection with human immunodeficiency virus (HIV), hepatitis B virus (HBV) or hepatitis C virus (HCV). Patients who are seropositive because of hepatitis B virus vaccine are eligible.
- 3.2.10 Major surgery within 4 weeks of enrollment.
- 3.2.11 Myeloma-related central nervous system involvement.
- 3.2.12 Known Amyloid involvement.
- 3.2.13 Participation in other clinical trials, including those with other investigational agents not included in this trial, within 30 days of the start of this trial and throughout the duration of this trial.
- 3.2.14 Prior CVA with persistent neurological deficit.
- 3.2.15 Inability to tolerate thromboprophylaxis.

3.3 Inclusion of Women and Minorities

- 3.3.1 Both men and women of all races and ethnic groups are eligible for this trial.

4. REGISTRATION PROCEDURES

4.1 General Guidelines for DF/HCC and DF/PCC Institutions

Institutions will register eligible participants in the Clinical Trials Management System (CTMS) OnCore. Registrations must occur prior to the initiation of protocol therapy. Any participant not registered to the protocol before protocol therapy begins will be considered ineligible and registration will be denied.

CONFIDENTIAL

This document is confidential. Do not disclose or use except as authorized.

An investigator will confirm eligibility criteria and a member of the study team will complete the protocol-specific eligibility checklist.

Following registration, participants may begin protocol therapy. Issues that would cause treatment delays should be discussed with the Overall Principal Investigator (PI). If a participant does not receive protocol therapy following registration, the participant's registration on the study must be canceled. Registration cancellations must be made in OnCore as soon as possible.

4.2 Registration Process for DF/HCC and DF/PCC Institutions

DF/HCC Standard Operating Procedure for Human Subject Research Titled *Subject Protocol Registration* (SOP #: REGIST-101) must be followed.

4.3 General Guidelines for Other Investigative Sites

The Research Project Manager will enter eligible participants on study at DFCI. All sites should call or email the Research Project Manager, to ensure enrollment availability prior to consenting any patients.

Following registration, participants should begin protocol therapy as soon as feasible. Issues that would cause treatment delays should be discussed with the Overall PI. If a participant does not receive protocol therapy following registration, the participant's registration on the study must be canceled. The Research Project Manager should be notified of cancellations as soon as possible.

4.4 Registration Process for Other Investigative Sites

To register a participant, the following documents should be completed by the research nurse or data manager and e-mailed to the Research Project Manager:

- Copy of labs and clinical information that satisfy inclusion criteria
- Signed participant consent form
- HIPAA authorization form
- Registration Form

The research nurse or data manager at the participating site will then call or e-mail the Research Project Manager, to verify eligibility. To complete the registration process, the Research Project Manager will follow DF/HCC Standard Operating Procedure for Human Subject Research Titled *Subject Protocol Registration* (SOP #: REGIST-101) and register the participant on the protocol. The Research Project Manager will fax or e-mail the participant study number, and if applicable the dose treatment level, to the participating site. The coordinator will also call the research nurse or data manager at the participating site and verbally confirm registration

Treatment may not begin without confirmation from the Coordinating Center that the participant has been registered.

CONFIDENTIAL

This document is confidential. Do not disclose or use except as authorized.

NOTE: Registration with the coordinating center can only be conducted during the business hours of 8:00 AM and 5:00 PM Eastern Time Monday through Friday. Same day treatment registrations will only be accepted with prior notice and discussion with the study team at DFCI.

5. TREATMENT PLAN

5.1 Treatment Regimen

Treatment will consist of 6 cycles of induction therapy followed by maintenance therapy for a total of 12 months. A treatment cycle is defined as 28 consecutive days.

For treatment cycles 1 through 12, a +/- 7 day window for nivolumab dosing is allowed. For further guidance on lenalidomide and dexamethasone holds and delays, please see Table 17. No investigational or commercial agents or therapies other than those described below may be administered with the intent to treat the participant's malignancy.

** As of September 2017, the trial has been put on partial clinical hold by the Food and Drug Administration: all patients are to discontinue nivolumab indefinitely, and no additional patients will be accrued to the trial. Participants may elect to remain on lenalidomide/dexamethasone or lenalidomide therapy alone for disease control after discussion with the overall PI.

Induction Cycles

Table 7: Nivolumab and Lenalidomide and Dexamethasone Combination (Cycles 1-6)

Agent	Pre-medications/ Precautions	Dose	Route	Schedule	Cycle Length
Nivolumab	None	240 mg	Intravenous	Days 1,15	28 days
Lenalidomide	None	25 mg	Oral	Days 1-21 of each cycle	
Dexamethasone	Take with food; Recommended to be taken in the morning	40 mg	Oral	Days 1, 8, 15	

Maintenance Cycles**

Table 8: Nivolumab and Lenalidomide Combination (Cycles 7-12)

Agent	Pre-medications/ Precautions	Dose	Route	Schedule	Cycle Length
Nivolumab	None	240 mg	Intravenous	Days 1, 15	28 days
Lenalidomide	None	15 mg*	Oral	Days 1-21 of	

CONFIDENTIAL

This document is confidential. Do not disclose or use except as authorized.

				each cycle	
--	--	--	--	------------	--

* If patient was dose reduced during the induction phase for lenalidomide below 15mg, then maintenance phase starts at that dose reduction and not at the higher 15 mg dose.

** During maintenance, if a patient experiences biochemical progression ($\geq 25\%$ increase and an absolute increase of $\geq 0.5\text{g/dL}$ from their nadir in their serum or urine m-spike or FLC with no CRAB features attributable to MM progression) high-dose dexamethasone may be re-added to the combination at a dose of 40mg oral given on days 1, 8, and 15 of a 28 day cycle after discussion with the overall PI.

The participant will be requested to maintain a medication diary. The medication diary should be returned to clinic staff at the end of each cycle.

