1.3 Duration of Study

A treatment cycle is defined as 28 consecutive days.

Patients will receive 6 cycles of induction therapy followed by 6 cycles of maintenance therapy with lower doses of lenalidomide and no dexamethasone for a total of 12 months.

During maintenance, if a patient experiences biochemical progression ($\geq 25\%$ increase and an absolute increase of $\geq 0.5\text{g/dL}$ from their nadir in their serum or urine m-spike or FLC with no CRAB features attributable to MM progression) high-dose dexamethasone may be re-added to the combination at a dose of 40mg oral given on days 1, 8, and 15 of a 28 day cycle after discussion with the overall PI.

For all treatment cycles a $+\text{-} 7$ day window is allowed for Nivolumab. For hold and delay guidelines for lenalidomide and dexamethasone, please refer to Table 17. The treatment plan is designed to be administered on an outpatient basis, however if necessary, may be given as inpatient.

Patients will be followed for up to three years after discontinuation of therapy.

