2.9.1 Dexamethasone effect on immune response

The use of dexamethasone in this study may blunt the immune response to Nivolumab. However, all prior studies of lenalidomide and dexamethasone in smoldering myeloma have used the combination of both agents. Therefore, to assess the true significance of adding Nivolumab to this combination, we will not omit dexamethasone from the regimen. In addition, recent studies in MM have shown that pulse dexamethasone used in our regimens of myeloma does not significantly blunt the immune response⁴¹. Moreover, recent studies in relapsed myeloma have shown preliminary strong activity of immune-mediated antibodies in combination with lenalidomide and dexamethasone. Moreover, we will monitor for immune cell numbers and checkpoint regulation on immune cells at the start of therapy and during therapy to define the effect of these agents on immune regulation. If patients cannot tolerate dexamethasone, then dose reductions will be permitted as described in dose reduction/modification sections.

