5.2.3 Dexamethasone

Dexamethasone will be obtained from commercial supply in this study. This may lead to added costs for the participant or the participant's insurance company.

Dexamethasone will be given as a single oral dose of 40mg on days 1, 8, and 15 of each 28 day cycle during the induction phase of this study (Cycles 1-6 only).

Dexamethasone should be taken at approximately the same time each day. It is recommended that dexamethasone be taken in the morning to reduce insomnia. Each dose should be taken with food. If a dose of dexamethasone is vomited, the participant should continue with the regular schedule of the drug at the next dose. If a dose is missed and less than 12 hours has elapsed since the missed dose, the patient may take the dose for that day. If more than 12 hours has elapsed since missing a dose at the normal time, the patient should not take the dose, but take the next dose at the normal time on the following day. If a dose is missed, it should be taken as soon as possible on the same day. If a dose is vomited, the dose should not be made up and the participant should continue with the regular schedule of the drug at the next dose.. A drug diary must be provided to participants to record oral administration of doses. Dose modification guidelines are described in Section 6.3.

CONFIDENTIAL

This document is confidential. Do not disclose or use except as authorized.

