6.4 Dexamethasone

Dexamethasone Dose Modifications

For adverse events that are considered to be possibly, probably or definitely related to dexamethasone, the following criteria for retreatment and dose modification should be followed unless discussed and approved first by the Overall Principal Investigator. The treating investigator should determine the clinical significance and attribution of the toxicity to dexamethasone. If toxicity is unlikely or not related to dexamethasone, do not omit or reduce therapy. Patients may continue on study if dexamethasone has been permanently discontinued

Table 15 Dexamethasone Dose Modifications

CTCAE 4.0 Category	CTCAE Grade	Dexamethasone Dose Modification
Hyperglycemia	Grade 1	Continue to treat- Do NOT OMIT and DO NOT

CONFIDENTIAL

This document is confidential. Do not disclose or use except as authorized.

Treat with oral medication or insulin at discretion of treating investigator		REDUCE therapy
	Grade 2	Hold dexamethasone until < Grade 2 and resume at same dose level at the discretion of the treating investigator
	Grade 3	Hold dexamethasone until < Grade 2 Resume therapy with one dose level reduction at the discretion of the treating investigator
	Grade 4	Hold dexamethasone until < Grade 2 Resume therapy with one dose level reduction
Symptomatic pancreatitis	Any Grade	Discontinue dexamethasone permanently

OTHER	Grade 1 or 2	Continue to treat- Do NOT OMIT and DO NOT REDUCE therapy
	Grade 3	Hold dexamethasone until \leq Grade 2 Resume therapy with one dose level reduction
	Grade 4	Hold dexamethasone \leq Grade 2 Resume therapy with one dose level reduction

If the patient discontinues dexamethasone prior to maintenance, he or she is not required to come off protocol therapy.

Table 16 Dexamethasone Dose Reduction

Dose Level	Dexamethasone Dose
0	40 mg
-1	20 mg
-2	10 mg

If dexamethasone is reduced for any toxicity, the dose may not be re-escalated.

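### Dexamethasone re-addition in maintenance is given at 40 mg only, with no carry-over of earlier toxicity reductions and no link to Section 6.4

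*Combined protocol and SAP*

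**What the plan says.** Section 1.3 plans "6 cycles of maintenance therapy with lower doses of lenalidomide and no dexamethasone". Section 1.3 and footnote ** to Table 8 in Section 5.1 then allow an exception for biochemical progression without CRAB features: "high-dose dexamethasone may be re-added to the combination at a dose of 40mg oral given on days 1, 8, and 15". The only step required beforehand is that the overall PI be consulted. The dose is the same in both places, and neither refers to Section 6.4.

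Section 6.4 sets three dexamethasone levels in Table 16: 40, 20 and 10 mg. Below that table it states: "If dexamethasone is reduced for any toxicity, the dose may not be re-escalated". Its opening paragraph says that the retreatment and dose-modification criteria "should be followed unless discussed and approved first by the Overall Principal Investigator". Table 15 requires permanent discontinuation after symptomatic pancreatitis.

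Three other places bear on the point:
- Footnote * to Table 8 deals with lenalidomide: "If patient was dose reduced during the induction phase for lenalidomide below 15mg, then maintenance phase starts at that dose reduction".
- Section 5.2.3 confines scheduled dexamethasone to dosing "during the induction phase of this study (Cycles 1-6 only", and the nursing page does the same. Section 1.3 and footnote ** are therefore the only dosing instruction for re-addition.
- Section 2.9.1 foresees intolerance: "If patients cannot tolerate dexamethasone, then dose reductions will be permitted as described in dose reduction/modification sections". It names no dose level. The nursing page does list 20 and 10 mg as reduced doses.

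**The concern.** Consider a patient whose dexamethasone was lowered to 20 or 10 mg for toxicity in induction, stopped as planned after cycle 6, and then progressed biochemically in maintenance. The instruction written for that moment offers 40 mg and nothing else. The section on dose modification says that a reduced dose may not go back up. No text states which one governs.

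The consent step differs too. Footnote ** asks for discussion with the overall PI. A departure from Section 6.4 needs discussion and prior approval. A site could complete the first without obtaining the second, and nothing in the footnote prompts it to mention an earlier reduction. At stake is a return to a dose that has already led to a toxicity reduction in that patient.

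**Working it through.** The protocol gives no figure of its own to reproduce. The check sets the texts side by side and then does the dose arithmetic.

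**Which text applies to whom**

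| Dexamethasone history in induction | Section 1.3 and footnote ** | Section 6.4 |
|---|---|---|
| Never reduced | 40 mg after PI discussion | No restriction |
| Reduced to 20 mg for toxicity | 40 mg after PI discussion | No increase unless PI approves first |
| Reduced to 10 mg for toxicity | 40 mg after PI discussion | No increase unless PI approves first |
| Permanently discontinued (pancreatitis) | Not mentioned | Barred by Table 15 |

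The two sources agree in the first row only. In the other rows the reader must infer that Section 6.4 limits the footnote. The same inference serves all three: if Table 15 governs the footnote without a cross-reference, so does the bar on re-escalation.

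**Size for a reduced patient**

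Inputs: 40 mg on days 1, 8 and 15, so 3 doses per 28-day cycle (footnote **); reduced levels of 20 and 10 mg (Table 16); maintenance cycles 7 to 12, so 6 cycles (Table 8).

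- Ratio to the last permitted dose: 40/20 = 2 and 40/10 = 4.
- Per cycle at 40 mg: 3 × 40 = 120 mg.
- Per cycle at 20 mg: 3 × 20 = 60 mg, so the excess is 120 − 60 = 60 mg.
- Per cycle at 10 mg: 3 × 10 = 30 mg, so the excess is 120 − 30 = 90 mg.
- Worst-case bound over maintenance: 6 × 60 = 360 mg (20 mg level) or 6 × 90 = 540 mg (10 mg level).

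The last line assumes re-addition from cycle 7 day 1 and every dose taken. It is an upper bound, not an expected exposure. With a single cycle of re-addition the excess is 60 or 90 mg.

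**Who could be affected**

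A patient must have had a dexamethasone reduction for toxicity and must then progress biochemically in maintenance. The documents give no rate for either event, so no number is estimated. Section 5.1 records that accrual closed in September 2017, so the group is fixed and may be empty. The same paragraph lets participants stay on lenalidomide with dexamethasone, so the hold does not by itself remove the issue.

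**The case against.** A reader might infer that the protocol contradicts itself, or directs an excessive dose. The documents do not support that. Footnote ** is permissive and Section 6.4 is a prohibition, so a site that withholds 40 mg from a reduced patient complies with both. Table 7, Section 5.2.3 and Section 8.3.7 also state 40 mg for induction without excepting reduced patients, and those doses are plainly subject to Section 6.4. Footnote ** can be read the same way, and Section 2.9.1 supports this by sending dexamethasone intolerance to the dose-modification sections.

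The lenalidomide comparison has limits. Every patient entering maintenance is assigned 15 mg of lenalidomide, so footnote * is needed to stop an automatic increase. Dexamethasone has no scheduled maintenance dose, and its re-addition is optional and discussed case by case. The overall PI is the gatekeeper under both texts and may approve a departure.

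It could also be argued that restarting after the planned stop at cycle 6 is not re-escalation at all. The protocol does not say this, and for lenalidomide it carries a reduction below 15 mg across that same boundary.

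Most of this stands, and it makes the point smaller. It does not close it. The nominal reading has to be inferred, a single fixed dose labelled as high-dose invites a literal reading, and discussion is a lower bar than prior approval.

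**Conclusion.** The point holds as a minor safety inconsistency. The only stated re-addition dose is 40 mg, earlier toxicity reductions are not carried forward, and the rule that limits them is not cited. Taken literally, and after PI discussion alone, a previously reduced patient could receive 2 or 4 times the last permitted dose, an excess of 60 or 90 mg per cycle. This rests on a literal reading of footnote **; under the nominal reading there is no excess.

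Practical risk is small, because the step is optional, the overall PI is consulted and the affected group is narrow and closed. The dose wording leaves the 2-year progression-free endpoint, the rule of 24 of 39 patients and the stated error probabilities in Section 13.1 as they are.

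**What to change.** In Section 1.3 and in footnote ** to Table 8, state that dexamethasone may be re-added at 40 mg or, if it was reduced for toxicity, at no more than the last tolerated Table 16 level. Make this expressly subject to Section 6.4, with no re-addition after permanent discontinuation. Any higher dose would then need the Overall PI's prior approval, as Section 6.4 already requires.

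A clerical correction can go with it: Section 5.2.3 refers to Section 6.3, the lenalidomide section, for dexamethasone dose modification, and should refer to 6.4. Section 5.2.3.1 already cites 6.4 for delays and interruptions, so this is a typographical matter only.

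The cost is one clause in two places and one section number. Sample size, visits and analysis do not change.

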5.2 Agent Administration

The drugs may be administered in any order.

5.2.1 Nivolumab

5.2.1.1 Administration

Nivolumab will be administered at a dose of 240 mg as an intravenous infusion over 60 minutes (+/- 10 minutes) every 2 weeks (Days 1 and 15 of each 28 day cycle).

See section 8.1.7 for guidelines on drug preparation and section 8.1.8 for further guidelines for drug administration.

Administer the infusion over 60 minutes (+/- 10 minutes) through an intravenous line containing a sterile, non-pyrogenic, low protein binding in-line filter (pore size of 0.2 micrometer to 1.2 micrometer).

Do not co-administer other drugs through the same intravenous line.

Flush the intravenous line at end of infusion.

5.2.1.2 Dose Delay or Interruption

Please refer to section 6.2 of the protocol.

5.2.2 Lenalidomide

Lenalidomide will be obtained from commercial supply in this study. This may lead to added costs for the participant or the participant's insurance company.

Lenalidomide will be given as a single daily oral dose of 25 mg per day on days 1-21 followed

CONFIDENTIAL

This document is confidential. Do not disclose or use except as authorized.

by a 7-day rest period for induction (cycles 1-6) and 15 mg per day on days 1-21 for maintenance (cycles 7-12) (if a patient was dose reduced during the induction phase for lenalidomide below 15mg, then maintenance phase starts at that dose reduction and not at the higher 15 mg dose). Please refer to Table 17 for specific hold and delay instructions for lenalidomide. Dose modification guidelines are described in Section 6.3.

Lenalidomide capsules should be swallowed whole, and should not be broken, chewed or opened. Administration of lenalidomide should be at approximately the same time each day. Drug may be taken with or without food. If a dose is missed and less than 12 hours has elapsed since the missed dose, the patient may take the dose for that day. If more than 12 hours has elapsed since missing a dose at the normal time, the patient should not take the dose, but take the next dose at the normal time on the following day. If a dose is missed, it should be taken as soon as possible on the same day. If a dose is vomited, the dose should not be made up and the participant should continue with the regular schedule of the drug at the next dose. A drug diary must be provided to participants to record oral administration of doses.

Participants who take more than the prescribed dose of lenalidomide should be instructed to seek emergency medical care if needed and contact study staff immediately. Participants experiencing adverse events may need study treatment modifications (see Section 6.3).

Lenalidomide related resources must be provided to all patients prior to receiving lenalidomide therapy as part of the Revlimid REMS program. For more information regarding program registration and drug ordering, refer to section 8.2.

